1.0 INTRODUCTION/BACKGROUND

Brain metastases are the most common adult intracranial tumor, occurring in approximately 10% to 30% of adult cancer patients, and represent an important cause of morbidity and mortality in this population.¹ The risk of developing brain metastases differs with different primary tumor histologies, with lung cancer accounting for approximately one half of all brain metastases.² The prognosis of patients with brain metastases is poor. The median survival time of untreated patients is approximately 1 month.³ With treatment, the overall median survival time after diagnosis is approximately 4 months.⁴ The RTOG recursive partitioning analysis (RPA) describes three prognostic classes, defined by age, Karnofsky Performance Score (KPS), and disease status.⁵ The most widely used treatment for patients with multiple brain metastases is WBRT. The appropriate use of WBRT can provide rapid attenuation of many neurological symptoms, improve quality of life, extend median survival, and be especially beneficial in patients whose brain metastases are surgically inaccessible or when other medical considerations preclude surgery.^{6,7} The use of adjuvant WBRT after resection or stereotactic radiosurgery (SRS) has been proven to be effective in terms of improving local control of brain metastases, and thus, the likelihood of neurological death is decreased.⁸

The majority of patients who achieve local tumor control die from progression of extracranial disease, whereas the cause of death is most often due to CNS disease in patients with recurrent brain metastases.^{7,8} Currently, no consensus on the optimal radiation schedule for patients with brain metastases is established. Standard treatment regimens include dose fractionation schemes evaluated in the early RTOG studies and range from 20 Gy in 5 fractions to 40 Gy in 20 fractions. The exact regimen used is generally at the discretion of the treating physician and often depends upon issues such as the severity of CNS symptoms, the extent of systemic disease, and physician preference.

More recently, a phase III randomized study (RTOG 9508) found that the combination of WBRT and SRS boost was superior to WBRT alone in selected patients.⁹ On this study, patients with a solitary brain metastases had an overall survival benefit when SRS was given. Furthermore, patients in the SRS group were more likely to have a stable or improved Karnofsky Performance Status (KPS) score at 6 months follow-up than were patients allocated WBRT alone. Intracranial disease control and use of steroids were also improved with SRS in patients with multiple brain metastasis.⁹ While the benefits of improved local control gained by adding SRS to WBRT are clear, many factors continue to limit the use of SRS. This procedure is generally contraindicated in lesions larger than 3-4 cm in size. In addition, while multiple lesions can be treated with SRS, the procedure can quickly become unwieldy as the number of lesions increases and dosimetric considerations may also start to increase the risk of toxicity.

RapidArc (RA) (Varian Medical Systems, Palo Alto, CA) is a volumetric modulated arc technique that uses a single 358 degree rotation of the linear accelerator to deliver highly conformal intensity modulated three dimensional dose distributions. The combination of accurate and reproducible patient setup prior to treatment with a RA plan provides an alternative to conventional SRS by allowing for integration of the WBRT with fractionated SRS-like boost. A recent publication generated composite RA plans consisting of WBRT with an integrated boost to gross brain metastases. These RA plans were then measured in a solid water phantom. It was also clinically delivered in 3 patients. The generated plans demonstrated excellent PTV coverage with a steeper dose gradient outside of brain metastasis as well as higher conformity index than WBRT followed by SRS.¹⁰ A similar experience was recently published describing WBRT with simultaneous infield boost using helical tomotherapy. Generated plans demonstrated similar target coverage with improved critical tissue sparing in patients with one to three metastatic brain metastases.¹¹ RapidArc delivery allows for giving differential, highly conformal, radiation doses to different portions of the brain. With conventional WBRT, the entire brain is treated to the "macroscopic disease dose" due to the inability with conventional fields to selectively deliver dose to specific areas of the brain. The conventional "macroscopic disease" dose is typically 30 Gy in 10 fractions or 37.5 Gy in 15 fractions. Several studies have indicated that patients at high risk of brain involvement, but without gross brain metastases, achieve high levels of intracranial control with lower "prophylactic disease" doses. The typical prophylactic cranial irradiation (PCI) dose for lung cancer is 25 Gy in 10 fractions. RTOG 0214 randomized patients with locally advanced non-small cell lung cancer status post definitive therapy to PCI or not.¹² These patients are known to be at high risk of brain metastases, up to 25% at 2 years. PCI reduced the 1 year incidence of brain metastases significantly from 18% to 8%. With RapidArc technology, the whole brain at risk could be given a reduced PCI dose, while the gross disease seen on MRI can be boosted with higher doses known to lead to better local control. We feel that the reduced whole brain dose allowed by this technique would lead to similar rates of distant brain control as conventional dosing, but with the possibility of reduced neurocognitive toxicity, as critical structures such as the white matter tracts and hippocampi will receive lower radiation doses.

Varian Medical Systems has notified and received clearance from the Food and Drug Administration (FDA) to use RapidArc in patient care. This technology is not considered an experimental device. The standard of care for patients with 1 – 4 brain metastases is currently WBRT with or without SRS boost. Patients with more than 4 brain metastases are typically eligible for WBRT only. With an integrated boost method, we believe that we can deliver increased dose to the gross disease, in a more convenient and time efficient manner, include patients who would not otherwise be SRS candidates, and spare more normal brain tissue, which may translate into improved local control and median survival. We believe that the risk:benefit ratio is favorable for patients who would be enrolled on this study due for several reasons: the current very poor prognosis of the condition, the use of an existing FDA approved technology, and the integration of a proven treatment into a more efficient regimen.

Given the limitations of the SRS boost technique, the purpose of our investigation is to evaluate an alternative strategy for giving WBRT with highly focal boost to gross visible lesions in patients with brain metastasis. In this study, we plan to assess the tolerability of using volumetric modulated arc therapy (RapidArc) on patients with brain metastasis to simultaneously treat the entire brain with a concomitant focal boost to grossly identified lesions on MRI scan to try to improve local control and reduce neurocognitive toxicities.

This previous version of this study was a phase I dose escalation trial giving 25 Gy in 10 fractions to the whole brain with simultaneous infield boost (SIB) to a total of 45 Gy in 10 fractions to gross brain metastatic disease. Prior to this, patients were enrolled onto one of two cohorts with whole brain dose of 30 Gy in 10 fractions with SIB to total of 45 Gy in 10 fractions to gross brain metastatic disease or whole brain dose of 37.5 Gy in 15 fractions with SIB to total of 52.5 Gy in 15 fractions to gross brain metastatic disease. A total of 12 patients have been previously enrolled on this trial. No patients have experienced a dose limiting toxicity (grade 3 or above) at least possibly due to study therapy. Also, no patients experienced local brain failure/progression at a site of treated metastatic brain disease. Based on this, we no longer feel that dose escalation to the gross brain disease is warranted and would proceed with a single arm pilot study treating patients with 25 Gy in 10 fractions to the whole brain with simultaneous infield boost (SIB) to a total of 45 Gy in 10 fractions to gross brain metastatic disease.

2.0 OBJECTIVES

2.1 Primary Objectives

- 2.1.1 To determine the feasibility of treating brain metastasis patients with whole brain radiation and simultaneous focal boost using an RA technique. (see Section 11.4)
- 2.1.2 To determine the locoregional control [at visible lesion(s) and new site(s)] in the brain of patients treated with a concomitant boost RA plan.

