11.3.2 Brain metastasis size evaluation

The treating radiation oncologist will measure and calculate the volume for each brain metastasis identified as a contrast enhancing mass on MRI at baseline using radiation oncology treatment planning software. This value will be recorded on the baseline form and every subsequent follow-up form. The appearance (yes/no) of any new brain metastases will be recorded on all follow-up forms.

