11.3.4 Definition of CNS progression

CNS progression will be defined as a > 25% increase in volume for any tracked brain metastasis, or the appearance of any new brain metastasis on a follow-up MRI. For lesions smaller than 1 cm in maximum diameter, a maximum increase of 50% in volume will be necessary to score as progression. This caveat is included to account for potential variability in measurement, which will be most susceptible to proportionate errors at smaller sizes. For greater than 1 cm lesions, the definition will use a 25% rule for change.

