12.2 Criteria for patient to be considered off study

- 12.1.1 Local CNS disease progression.
- 12.1.2 Patient death.
- 12.1.3 Patient request to come off study.
- 12.1.4 Patient is discharged to hospice

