13.0 STATISTICAL CONSIDERATIONS

13.1 Study endpoints

13.1.1 Primary endpoints

- Feasibility – Measurement of the amount of time required for daily treatment
- Rates of toxicities
- Local brain control
- Regional brain control

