13.3 Statistical Analysis

Descriptive statistics will be performed on the clinical and treatment factors on subjects on this study. Categorical data will be presented on frequency tables while continuous data will be presented as mean, standard deviation, median and range. Local control, regional brain control, progression-free survival and overall survival will be assessed using the Kaplan-Meier method with censoring as appropriate. Univariate and multivariate analysis will be performed with these endpoints to determine patient factors that may influence outcome. These curves will also be compared to previously published results as historical controls. The results of the neurocognitive and quality of life surveys/tests will be plotted for each patient to assess for a general trend over time. The trend over time can also be analyzed by linear regression analysis. Each point in time can be compared with historical controls using a student's t-test to determine whether there is a significant difference in the survey/test scores in patients on our study versus historical results.

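### No combined locoregional analysis is specified for objective 2.1.2, and the off-study rule at local progression may bias the separate regional-control curve upwards

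*Combined protocol and SAP*

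**What the plan says.** Section 2.1 gives the second primary objective as "To determine the locoregional control [at visible lesion(s) and new site(s)] in the brain of patients treated with a concomitant boost RA plan".

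Section 13.1.1 lists "Local brain control" and "Regional brain control" as separate primary endpoints. Section 13.3 states: "Local control, regional brain control, progression-free survival and overall survival will be assessed using the Kaplan-Meier method with censoring as appropriate". It names no combined locoregional curve and gives no censoring rule.

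Section 11.3.4 defines CNS progression as growth of a tracked lesion beyond a volume threshold, "or the appearance of any new brain metastasis on a follow-up MRI". That is a composite of local and new-site failure, but no objective or endpoint refers to it. Progression-free survival is a secondary endpoint and is not defined.

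The component data are collected. Section 11.3.2 says: "The appearance (yes/no) of any new brain metastases will be recorded on all follow-up forms". Section 11.3.3 has each treated lesion's volume measured at every study MRI.

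Section 12.2, within the Data Collection section, lists "Local CNS disease progression" as an off-study criterion, alongside death, patient request and discharge to hospice. A new lesion on its own is not listed. The section does not say what is recorded after a patient comes off study.

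**The concern.** There are two distinct problems.

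- **Objective and analysis.** The objective names locoregional control, covering visible and new sites. The analysis section names its two parts only. A reader given a local curve and a regional curve cannot work out what proportion of patients were free of any brain failure, because that depends on how far the two kinds of failure fall in the same patients. The plan does not say whether one composite or two components is intended.
- **Regional curve.** If recording stops at local progression, a patient whose treated lesion grows is censored for regional control at that moment, and later new lesions go unseen. Kaplan-Meier is then valid only if such patients have the same later risk of new lesions as those who remain. Local and distant brain failure probably share causes, so the curve would tend to read too high. That direction favours the rationale in section 1.0, which expects the reduced whole-brain dose to give distant control similar to conventional dosing. Section 13.3 also compares these curves with published historical results.

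**Working it through.** The plan gives no target rate, precision or power for these endpoints, so there is no figure to reproduce. The check concerns the structure, with assumed rates used to size it.

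**Step 1: what two curves say about the combined figure.** Let L and R be the 12-month local and regional failure probabilities. Combined control lies between max(0, 1 − L − R), when no patient fails in both ways, and min(1 − L, 1 − R), when failures overlap as far as possible.

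- L = 10%, R = 30% (assumed): 1 − 0.10 − 0.30 = 0.60, up to min(0.90, 0.70) = 0.70.
- L = 20%, R = 40% (assumed): 1 − 0.20 − 0.40 = 0.40, up to min(0.80, 0.60) = 0.60.

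Multiplying the two curves works only under independence. In the simulation below, at 20% and 40% with correlation 0.8, the product is 0.480 while combined control is 0.580.

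**Step 2: effect of leaving the study at local progression.** The simulation used 400,000 patients per scenario. Local and regional failure times were exponential and linked by a Gaussian copula with correlation ρ. Death was independent with a median of 8 months, and follow-up was cut at 24 months. All rates, ρ and the 8 months are assumptions; the documents give none of them. The entries are Kaplan-Meier control at 12 months, with deaths censored.

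| Local / regional failure | ρ | Combined, full follow-up | Combined, off study at local | Regional, full follow-up | Regional, off study at local | Regional shift |
|---|---|---|---|---|---|---|
| 5% / 20% | 0 | 0.761 | 0.761 | 0.801 | 0.801 | 0.000 |
| 5% / 20% | 0.5 | 0.781 | 0.781 | 0.801 | 0.809 | 0.008 |
| 5% / 20% | 0.8 | 0.795 | 0.795 | 0.800 | 0.810 | 0.010 |
| 10% / 30% | 0 | 0.630 | 0.630 | 0.700 | 0.700 | 0.000 |
| 10% / 30% | 0.5 | 0.666 | 0.666 | 0.701 | 0.716 | 0.015 |
| 10% / 30% | 0.8 | 0.692 | 0.692 | 0.701 | 0.719 | 0.018 |
| 20% / 40% | 0 | 0.482 | 0.482 | 0.600 | 0.601 | 0.001 |
| 20% / 40% | 0.5 | 0.537 | 0.537 | 0.598 | 0.629 | 0.031 |
| 20% / 40% | 0.8 | 0.580 | 0.580 | 0.601 | 0.638 | 0.037 |
| 30% / 40% | 0 | 0.418 | 0.418 | 0.598 | 0.598 | 0.000 |
| 30% / 40% | 0.5 | 0.492 | 0.492 | 0.600 | 0.646 | 0.046 |
| 30% / 40% | 0.8 | 0.547 | 0.547 | 0.600 | 0.669 | 0.069 |

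The combined curve never moves. Local progression is itself an event for it, so leaving the study at that point loses nothing. The regional curve moves only when the failure types are correlated, and moves more as local failure becomes commoner.

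**Step 3: how common local failure might be.** Section 1.0 reports no local failure in 12 earlier patients. The exact 95% upper limit is 1 − 0.025^(1/12) = 0.265, about 26%. A rate near zero, where the bias vanishes, and a rate of 20% are both compatible with this. The 30% rows lie just outside that limit. Those patients came from mixed dose cohorts and their follow-up time is not stated.

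**Step 4: scale against 18 patients.** One patient is 1/18 = 5.6 points. If 14 of 18 are controlled (78%), the exact 95% interval is 52% to 94%. Sampling error is far larger than the bias.

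**The case against.** The strongest defence is that the objective's bracket names two kinds of site and the plan has one primary endpoint for each. The split also suits the design, since the boost is aimed at local control and the whole-brain dose at distant control. The investigators will hold patient-level data on both events, so the overlap is unknown only to someone shown the two curves. This stands in part: the two-component reading is tenable. But the plan does not say it is the one meant, and it defines a composite event that it then never uses.

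A reader might go further and infer that, because local progression ends follow-up, the objective's own quantity can never be estimated. The documents do not support that. The off-study rule leaves a first-event composite unchanged, the data to build it are collected, and the undefined progression-free survival endpoint might even draw on it. Nor does the plan say that follow-up ends. Section 12.2 says only that the patient is off study, 11.3.1 schedules MRI every 3 months without a stop at progression, and the overall survival endpoint implies some later follow-up. That data collection stops is an inference from where 12.2 sits and from the criteria beside it.

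The bias is also fairly called small and dependent on assumptions. The 7-point figure needs 30% local failure and a correlation of 0.8, and in a descriptive pilot of 18 patients even that is little more than one patient. This stands too, and limits how much weight the point carries.

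**Conclusion.** Two limited points hold. No combined locoregional analysis is specified for objective 2.1.2, although 11.3.4 supplies the event. And 12.2 leaves the primary regional-control curve open to informative censoring at local progression.

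The overstatement of 12-month regional control is about 1 to 7 points for local failure of 5% to 30%, regional failure of 20% to 40% and correlation of 0.5 to 0.8. It is nil under independence and negligible if local failure is near zero. It also depends on recording actually stopping at local progression, which the plan suggests but does not state. Neither point threatens the pilot. Both deserve correction because the regional bias is systematic, runs in the direction the rationale hopes for, and is cheap to remove.

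**What to change.** - **Sections 13.1.1 and 13.3.** Add time to first CNS progression as defined in 11.3.4, local or new-site, whichever comes first, as the locoregional analysis for objective 2.1.2. Report local and regional control as its components.
- **Death.** State for each of these curves how death without brain failure is handled. The present censoring wording leaves this open, and section 1.0 quotes a median survival of about 4 months with treatment, so deaths before brain failure may be frequent.
- **Section 12.2.** State that new-lesion status on any MRI done after local progression, and survival, are still recorded for the regional and overall survival analyses. This concerns recording only; it asks for no extra scans and does not alter patient management.

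Treating local progression as a competing event in the regional analysis is not an equivalent remedy. It would estimate new-site failure occurring before local failure, which is a different quantity from regional control.

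The cost is some wording, one more curve from data already collected, a little more recording, and a combined control figure that can be no higher than either component.

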2.2 Secondary Objectives

- 2.2.1 To determine the overall survival of brain metastasis patients treated with such an RA plan.

- 2.2.2 To determine the progression-free survival of brain metastasis patients treated with such an RA plan.
- 2.2.3 To assess the long-term neurocognitive effects of this treatment using the Hopkins Verbal Learning Test-Revised (HVLT-R), Mini Mental Status Exam (MMSE) and Cognitive Functioning Subscale of the Medical Outcomes Scale (MOS).
- 2.2.4 To assess quality of life (QOL) outcomes after this treatment using the quality of life questionnaire for the Functional Assessment of Cancer Therapy-Brain (FACT-Br).

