4.0 PRE-TREATMENT EVALUATION

- 4.1 MRI scan with and without contrast (at least 5mm resolution on T1 post-contrast imaging).
- 4.2 History and physical including a detailed neurologic exam.
- 4.3 Steroid and anti-convulsant doses must be documented.
- 4.4 Baseline MMSE.
- 4.5 Baseline neurocognitive function using the HVLT-R (memory).
- 4.6 Baseline neurocognitive function using MOS (self-report).
- 4.7 Baseline QOL assessment using FACT-Br.
- 4.8 Documentation of extent of systemic disease.
- 4.9 Pregnancy test in women of child bearing potential when there is clinical suspicion of pregnancy

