11.3 Toxicity and Outcome Assessments

11.3.1 Imaging followup

Patients will undergo brain MRI prior to study entry and at 1 month, 3 months and every 3 months thereafter or when otherwise indicated (eg. at onset of clinical deterioration). A window period of +/- 6 weeks will be allowed to correlate with each study time-point MRI.

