12.0 DATA COLLECTION

12.1 Data Fields

The following data will be collected on each patient: name, date of birth, medical record number, tumor characteristics by pathology of surgical specimen, radiologic results, performance status, radiation and chemotherapy treatment parameters, clinical outcome including local and regional control, overall survival, treatment complications, neurocognitive assessments, and QOL assessments.

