13.1.2 Secondary Endpoints (to be compared with standard historical controls)

- Progression-free survival
- Overall Survival
- Neurocognitive effects
- QOL outcomes

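### Progression-free survival is named without a site restriction, but the visible plan defines and schedules only CNS progression, so a comparison with published all-site PFS would be biased by the event definition

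*Combined protocol and SAP*

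**What the plan says.** The objective in 2.2.2 reads "To determine the progression-free survival of brain metastasis patients treated with such an RA plan". PFS appears again in 13.1.2, under the heading "Secondary Endpoints (to be compared with standard historical controls", and in 13.3, where it is estimated by Kaplan-Meier and its curve is set against published results. None of these places gives an event list, a site restriction, a time origin or a censoring rule, and no comparator is named.

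The only definition of progression is in 11.3.4: "CNS progression will be defined as a > 25% increase in volume for any tracked brain metastasis, or the appearance of any new brain metastasis". It is labelled CNS progression and is not linked to the PFS endpoint.

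On assessments, 11.3.1 says "Patients will undergo brain MRI prior to study entry and at 1 month, 3 months and every 3 months thereafter". The rest of section 11 covers cognition, quality of life, toxicity and treatment time. Systemic disease appears once, at pre-treatment (4.8): "Documentation of extent of systemic disease". The data fields in 12.1 include "clinical outcome including local and regional control, overall survival", but neither PFS nor extracranial progression. Section 12.2 takes a patient off study at local CNS progression, death, patient request or hospice discharge.

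Section 3.1.5 and Appendix A admit RPA class II patients, who may have extracranial metastases or an uncontrolled primary. Section 1.0 states: "The majority of patients who achieve local tumor control die from progression of extracranial disease".

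**The concern.** Without a qualifier, a reader will usually take PFS to mean progression at any site or death. The visible follow-up plan does not support that endpoint. It supports a narrower one, CNS progression or death.

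The mismatch matters because the PFS curve is to be compared with published curves. A patient whose systemic disease progresses while the brain stays controlled has an event in an all-site series and none here. Nothing in 13.1.2 or 13.3 prevents a comparator with the wider definition, and matching on prognosis would not remove a difference in what counts as an event. Part of any apparent PFS advantage could then come from the definition rather than the treatment.

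**Working it through.** **Plan's own figure.** There is none to reproduce. The documents give no PFS rate, median, event count, alpha or power, and the 18 patients are stated without a derivation.

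**Direction.** For each patient let C be time to CNS progression, E time to extracranial progression and D time to death.
- CNS-only PFS = min(C, D)
- All-site PFS = min(C, E, D)

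The second minimum is over a larger set, so min(C, D) ≥ min(C, E, D) for every patient, with strict inequality whenever E comes first. This needs no assumed rates. It compares two definitions in the same patients.

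**Size, on assumed rates.** None of these inputs is in the documents. All times are exponential with these medians in months:
- CNS progression, c: 6, 12 or 24
- extracranial progression, e: 3, 6 or 12
- death without progression: 24
- progression to death, p: 2 or 4

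Death is tied to progression because counting deaths recovers some of the extracranial events and narrows the gap.

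All-site median = 1 / (1/c + 1/e + 1/24).

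CNS-only survival: S(t) = 2^(−t(1/c + 1/24)) × [(1/p)·2^(−t/e) − (1/e)·2^(−t/p)] / (1/p − 1/e). The bracketed ratio is the probability that extracranial progression followed by death has not been completed by t.

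Mid-range case, c = 12, e = 6, p = 4:
- All-site median = 1 / (2/24 + 4/24 + 1/24) = 24/7 = 3.4 months.
- All-site share event-free at 6 months = 2^(−6 × 7/24) = 2^(−1.75) = 30%.
- CNS-only share at 6 months = 2^(−0.75) × (0.25 × 0.500 − 0.1667 × 0.3536) / 0.0833 = 0.595 × 0.793 = 47%.
- CNS-only median, solving S(t) = 0.5: 5.6 months. Ratio 5.6 / 3.43 = 1.63.

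| Case | c, e, p | All-site median | CNS-only median | Ratio | Gap (months) |
|---|---|---|---|---|---|
| Smallest ratio | 6, 12, 2 | 3.4 | 4.1 | 1.19 | 0.6 |
| Mid-range | 12, 6, 4 | 3.4 | 5.6 | 1.63 | 2.2 |
| Largest ratio | 24, 3, 4 | 2.4 | 5.6 | 2.34 | 3.2 |

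The other 15 combinations lie between these extremes. A simulation of 400,000 patients per combination gave the same ratios to within 0.01.

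**Precision.** If 9 of 18 patients are event-free at some time point, the exact 95% interval is about 26% to 74%.

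**The case against.** The strongest reply is that no comparator has been chosen. If the sponsor uses published brain-PFS results, this bias does not arise. That is correct, and it is why the point is conditional. What remains is that the plan does not require such a comparator.

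A reader might infer that the PFS objective cannot be met at all. The documents do not support that. The Appendix C grid is not visible, and 12.1 also lists radiologic results and chemotherapy parameters and introduces outcomes with an open-ended list, so scans from routine care may be captured. Even so, no visible section gives a criterion for extracranial progression or a schedule for assessing it.

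A reader might also infer that the reported PFS will always look longer than published PFS. That does not follow either. Case mix can move the observed gap either way, and so can the growth rule. For a sphere, a 25% volume increase is only a 7.7% increase in diameter (1.25^(1/3) = 1.077), so against a series with a looser rule the study could record progression earlier. Only the event-site component has a fixed direction.

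It is tempting, too, to say that extracranial disease drives the course in this population. Section 1.0 says so of patients with local control, and the same sentence attributes most deaths in recurrent brain metastases to CNS disease. The earlier cohorts had no local failures among 12 patients, which makes the local-control group relevant, but the statement is not general.

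Finally, PFS is a secondary endpoint of an 18-patient pilot with no decision rule attached. That limits the consequence. Imprecision does not, however, cancel an error that runs in one direction.

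**Conclusion.** The point holds in conditional form. The visible text defines and schedules CNS progression only, while 2.2.2, 13.1.2 and 13.3 use an unrestricted PFS and compare it with published results. What the analysis can reliably deliver is time to CNS progression or death. Against a comparator that counts extracranial progression, the event definition alone lengthens PFS in like-for-like patients. Against an intracranial comparator there is no such effect.

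The direction of that component follows from the definitions. Its size cannot be obtained from the documents. The ratio of roughly 1.2 to 2.3, or 0.6 to 3.2 months at the median, rests entirely on assumed exponential rates and is an illustration, not a bound. The change is worth making but is not critical to the trial.

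**What to change.** In 2.2.2, 13.1.2 and 13.3, rename the endpoint 'intracranial progression-free survival: time to CNS progression per 11.3.4 or death from any cause', and state its time origin. In 13.1.2 and 13.3, restrict the historical comparison to published results that use an intracranial progression-or-death definition, and make no claim about all-site PFS.

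Renaming alone leaves one gap. Section 12.2 takes patients off study at hospice discharge, which can precede death, and 13.3 leaves censoring open. If those patients were censored at discharge, their deaths would be lost and the renamed endpoint would still be overstated. State that hospice discharge is not a censoring event for this endpoint and that vital status is still collected after it, except where the patient withdraws consent.

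The cost is a wording change plus vital-status follow-up after hospice discharge, with no new imaging. The downside is that fewer published series will qualify as comparators. Scheduling systemic assessment with an extracranial progression criterion would allow all-site PFS to be reported, but it costs more and the other objectives do not need it.
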